## **Statistical Methods**

### **Sample Size Calculation**

The sample size estimate is completed using the 95% confidence interval (CI) method. We propose a sample size of 50 patients. It generates a half-width of CI less than 10% if the blood clot rate is <15%. Since our study expects an 80% risk reduction in VTE, our estimated VTE rate is about 5%. If based on the 5% VTE incidence rate, the half-width CI will be <6%. Therefore, the precision will be improved with narrower CI, since we expect an incidence much lower than 15%.

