## **Protocol Summary**

**Title:** Apixaban for Primary Prevention of Venous Thromboembolism in Patients with Multiple Myeloma Receiving Immunomodulatory Therapy

**Design:** U.S.-based, single-center, single-arm, open-label, proof-of-concept study

**Brief Treatment Description:** Direct anti-factor Xa inhibition with apixaban 2.5 mg orally twice daily for primary prevention of VTE

**Purpose:** To determine the rate of major and clinically relevant non-major bleeding and the rate of symptomatic VTE in MM patients on immunomodulatory drugs (IMiDs) who are receiving apixaban 2.5 mg orally twice daily. This study will provide event rates that could inform the design of a larger randomized controlled trial.

**Population:** Outpatients with MM receiving IMiDs (i.e., thalidomide [Thalomid], lenalidomide [Revlimid], and pomalidomide [Pomalyst]).

**Enrollment:** 50 subjects

**Clinical Site Locations:** 1 center (Vanderbilt University Medical Center)

**Study Duration:** 22 months; enrollment period of up to 16 months with 6-month follow-up.

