## **Specific Aims**

Patients living with multiple myeloma (MM) have an increased risk of venous thromboembolism (VTE) due to the disease itself and the use of targeted therapies, including immunomodulatory drugs (IMiDs). Prevention of VTE has become a major management challenge during MM treatment. There is a paucity of data with respect to the non-vitamin K oral anticoagulants (NOACs) in the cancer population. However, the NOACs offer comparable efficacy but improved safety compared with warfarin. Apixaban has shown excellent safety and efficacy for treatment and prevention of recurrent VTE (1,2). The safety and efficacy of apixaban for primary prevention of VTE in MM patients has not been established.

**Aim #1:** To quantify the 6-month rate of major and clinically relevant non-major bleeding in MM patients receiving IMiDs who are prescribed apixaban 2.5 mg orally twice daily for primary prevention of VTE.

**Hypothesis #1:** The 6-month rate of major and clinically relevant non-major bleeding in MM patients receiving IMiDs who are prescribed apixaban 2.5 mg orally twice daily for primary prevention of VTE will be  $\leq 3\%$  (2). Although the MM population, in general, has a higher medical acuity than that of the previous large randomized controlled trials of apixaban, we will be selecting a stable population of MM patients who are appropriate for immunomodulatory therapy.

**Aim #2:** To quantify 6-month rate of symptomatic VTE in MM patients receiving IMiDs who are prescribed apixaban 2.5 mg orally twice daily for primary prevention of VTE.

**Hypothesis #2:** The 6-month rate of symptomatic VTE in MM patients receiving IMiDs who are prescribed apixaban 2.5 mg orally twice daily for primary prevention of VTE will be  $< 7\%$  (3). Although additional therapies for MM such as dexamethasone and erythropoietin-stimulating agents may further increase the risk of VTE, the rate of incident VTE should be reduced to  $< 7\%$  with apixaban.

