### **Study Objectives**

**Primary Safety Objective:** To quantitatively assess the 6-month rate of major and clinically relevant non-major bleeding in MM patients receiving IMiDs who are prescribed apixaban 2.5 mg orally twice daily for primary prevention of VTE.

**Primary Efficacy Outcome:** To quantitatively assess the 6-month rate of symptomatic VTE in MM patients receiving IMiDs who are prescribed apixaban 2.5 mg orally twice daily for primary prevention of VTE.

**Secondary Efficacy Outcome:** To quantitatively assess the 6-month rate of myocardial infarction and stroke.

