## **Safety Outcomes**

### **Primary Safety Outcome**

The primary safety outcome is the 6-month rate of major and clinically relevant non-major bleeding in MM patients receiving IMiDs who are prescribed apixaban 2.5 mg orally twice daily for primary prevention of VTE.

Using the ISTH classification, bleeding is defined as major if it is overt and associated with a decrease in the hemoglobin level of 2 g/dL or more, requires the transfusion of 2 or more units of blood, occurs into a critical site, or contributes to death (12).

Using the ISTH classification, clinically relevant nonmajor bleeding is defined as overt bleeding not meeting the criteria for major bleeding but associated with medical intervention, surgical intervention, or interruption of the study drug.

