### **Statistical Analysis Plan**

For this proof-of-concept study, we will calculate:

- 1) the 6-month rate of major and clinically relevant non-major bleeding
- 2) the 6-month rate of symptomatic VTE

We will also calculate 6-month rates of myocardial infarction and stroke.

The primary analysis will be intention-to-treat. Although study eligibility criteria warrant that the provider plans to treat the patient with IMiDs for at least 6 cycles, we will include any patient who has received at least 2 cycles in a modified intention-to-treat analysis.

Means, medians, and frequency distributions will be calculated for continuous variables. Number and percentages will be reported for binary and categorical variables. Differences between subgroups of interest will be examined using the chi-square or Fisher's exact test for binary and categorical variables and t-test or Wilcoxon Rank Sum for continuous variables (if the subgroups are of sufficient size for statistical comparison). Potential subgroup analysis will include patients newly diagnosed vs. recurrent/relapsed disease and concomitant medications (dexamethasone, etc.).

All tests will be two tailed and a p-value of <0.05 assumed to represent statistical significance. All analyses will be performed using SAS software.

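### n = 50 is justified only by confidence-interval width, yet the stated half-width below 6% is slightly optimistic and the analysis plan includes no interval for either primary rate

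*Combined protocol and SAP*

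**What the plan says.** All references are to the combined protocol and SAP.

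- **Sample Size Calculation.** The basis for n is interval width alone: "The sample size estimate is completed using the 95% confidence interval (CI) method", followed by "We propose a sample size of 50 patients". Two figures are given, both for VTE: a half-width under 10% if the rate is below 15%, and "If based on the 5% VTE incidence rate, the half-width CI will be <6" per cent. The type of interval is not named, and bleeding is not mentioned.
- **Statistical Analysis Plan.** The two 6-month rates, bleeding and symptomatic VTE, are to be calculated. For binary variables, "Number and percentages will be reported for binary and categorical variables". No confidence interval is planned for either rate.
- **Primary Safety Outcome.** "The primary safety outcome is the 6-month rate of major and clinically relevant non-major bleeding". The Specific Aims put this rate at no more than 3%.
- **Study Objectives and Protocol Summary.** The aim is estimation: "To quantitatively assess the 6-month rate of symptomatic VTE in MM patients receiving IMiDs", with a parallel objective for bleeding. The intended use is stated as "This study will provide event rates that could inform the design of a larger randomized controlled trial".

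**The concern.** A study whose sample size rests on interval width should say which interval it will report, and its stated width should come from that interval. Here the two sections do not connect: one sizes the study on a confidence interval, and the other plans none.

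The implied formula also matters at these rates. A 5% rate in 50 patients is 2.5 expected events and a 3% rate is 1.5. The Wald interval behaves poorly at such counts, above all at zero. If the interval is chosen only after the counts are known, the same result can be reported with quite different uncertainty. For a safety rate, Wald errs towards reassurance.

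**Working it through.** **Inputs.** n = 50, the 95% level, and rates of 15% and about 5% come from the Sample Size Calculation; 3% for bleeding comes from the Specific Aims. Two-sided intervals (z = 1.96) and all 50 patients in the denominator are assumed.

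**Step 1: reproduce the plan's figures.** The Wald half-width is z·√(p(1−p)/n).

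- p = 0.15: 1.96·√(0.15·0.85/50) = 9.90%, which agrees with the stated under 10%.
- p = 0.05: 1.96·√(0.05·0.95/50) = 6.04%, just above the stated bound. The n that gives 6% is 1.96²·0.05·0.95/0.06² = 50.7, so 51 instead of 50.

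Other standard intervals at a 5% rate give 6.23% (Jeffreys), 6.65% (Wilson) and 7.16% (Clopper-Pearson). Wald is therefore the likely source.

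**Step 2: which counts are likely?** Under a binomial model, the probability of 0 to 3 events is 76% at a true 5% and 94% at a true 3%. The probability of zero events is 0.95⁵⁰ = 7.7% and 0.97⁵⁰ = 21.8% respectively.

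**Step 3: limits at those counts.** The Wilson centre is (p + z²/2n)/(1 + z²/n), and its half-width is z·√(p(1−p)/n + z²/4n²)/(1 + z²/n). With n = 50, z²/n = 0.0768 and z²/4n² = 0.000384. For 1/50, the half-width is 1.96·√(0.000392 + 0.000384)/1.0768 = 5.07% and the centre is (0.02 + 0.0384)/1.0768 = 5.42%, giving 0.35 to 10.5%.

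| Events | Wald 95% limits | Wilson 95% limits | Half-width, Wald / Wilson |
|---|---|---|---|
| 0/50 | 0 to 0% | 0 to 7.1% | 0 / 3.6% |
| 1/50 | −1.9 to 5.9% | 0.35 to 10.5% | 3.9 / 5.1% |
| 2/50 | −1.4 to 9.4% | 1.1 to 13.5% | 5.4 / 6.2% |
| 3/50 | −0.6 to 12.6% | 2.1 to 16.2% | 6.6 / 7.1% |

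**Step 4: where Wald fails.** Exact coverage of the nominal 95% Wald interval is 92.0% at a true 5% and 78.1% at 3%. Zero events account for 7.7 of the 8.0 points of non-coverage at 5%, and for 21.8 of the 21.9 points at 3%. At 1 to 3 events the defects are impossible lower limits and lower upper limits.

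**Step 5: the 15% statement.** The largest count below 15% is 7/50. Wilson gives a half-width of 9.6% there and 9.9% at a rate of exactly 15%, so that sentence holds under Wilson. Clopper-Pearson gives 10.5% at 7/50, so under that method it does not.

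**The case against.** The strongest reply is that this is a proof-of-concept study in which no decision uses an interval. The Stopping Criteria are event counts, the analysis plan sets no test against a fixed rate, and anyone planning a later trial can compute an interval from the published count. All of that stands, and it keeps the point minor.

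It is also fair that the plan puts the VTE rate only at about 5%; at 4.9% the Wald half-width is 5.98%. Averaged over possible results at a true 5%, the expected half-width is 5.57% for Wald (lowered by its zero width at 0 events) and 5.96% for Jeffreys, but 6.45% for Wilson and 6.90% for Clopper-Pearson. So the stated figure can be defended on average for two of four methods.

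Three stronger readings are tempting, and the documents do not support them:

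- *That the trial will report Wald intervals.* Wald is inferred from the sizing figures. The plan names no formula and commits to no interval for reporting.
- *That Wald under-covers because 2 or 3 events are expected.* Step 4 shows that the shortfall comes almost entirely from the zero-event result.
- *That n is inadequate for bleeding because its precision is not stated.* At a true 3%, expected half-widths are 4.02% (Wald) to 5.77% (Clopper-Pearson), all below the 6% quoted for VTE. The omission is one of statement.

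**Conclusion.** The point holds as a minor inconsistency between sizing and analysis. The only quantity that justifies n = 50 is missing from the planned analysis, it is stated for one of two primary outcomes, and its value at 5% is slightly optimistic: 6.04% by Wald and 6.65% by Wilson, against a claim of under 6%. The practical effect is largest at 0 or 1 event, where the upper limit moves from 0% to 7.1% and from 5.9% to 10.5%.

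A reader might infer an arithmetic error that undermines the sample size. The documents do not support that: the Wald shortfall is one patient (51 against 50), and the 15% statement reproduces.

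The conclusion assumes two-sided 95% intervals, binomial counts and all 50 patients in the denominator. The limits would not apply to the modified intention-to-treat set (at least 2 cycles of IMiD therapy) if it is smaller.

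**What to change.** Keep n = 50 and use one interval throughout.

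1. **Sample Size Calculation.** Replace the sentence on the 5% rate with: *With 50 patients the two-sided 95% Wilson limits are 0–7.1% at 0 events, 0.35–10.5% at 1, 1.1–13.5% at 2 and 2.1–16.2% at 3 (half-width about 6.2–7.1% at 2–3 events); these apply to both primary outcomes when all 50 are in the denominator.* The sentence on rates below 15% can stay, labelled as Wilson.
2. **Statistical Analysis Plan.** Add: *Each primary rate will be reported with a two-sided 95% Wilson interval.*

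If Clopper-Pearson is preferred, its limits at 0 to 3 events are 0–7.1%, 0.05–10.65%, 0.5–13.7% and 1.3–16.5%, and the 15% sentence must then be restated as well (10.5% at 7/50).

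The cost is about two sentences, with no extra patients or data. The stated precision becomes slightly less favourable. Wilson coverage is 96.2% at a true 5% but slightly under nominal at 3% (93.7%); Clopper-Pearson avoids that but is conservative (98.8% at 5% and 98.3% at 3%).

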### **Statistical Analysis Plan**

For this proof-of-concept study, we will calculate:

- 1) the 6-month rate of major and clinically relevant non-major bleeding
- 2) the 6-month rate of symptomatic VTE

We will also calculate 6-month rates of myocardial infarction and stroke.

The primary analysis will be intention-to-treat. Although study eligibility criteria warrant that the provider plans to treat the patient with IMiDs for at least 6 cycles, we will include any patient who has received at least 2 cycles in a modified intention-to-treat analysis.

Means, medians, and frequency distributions will be calculated for continuous variables. Number and percentages will be reported for binary and categorical variables. Differences between subgroups of interest will be examined using the chi-square or Fisher's exact test for binary and categorical variables and t-test or Wilcoxon Rank Sum for continuous variables (if the subgroups are of sufficient size for statistical comparison). Potential subgroup analysis will include patients newly diagnosed vs. recurrent/relapsed disease and concomitant medications (dexamethasone, etc.).

All tests will be two tailed and a p-value of <0.05 assumed to represent statistical significance. All analyses will be performed using SAS software.

## **Investigator Responsibilities**

### **Study Initiation**

Before enrollment of the first subject at the study site, the following documents must be on file with the Study Sponsor:

1. Current *curriculum vitae* of the principal investigator and all co-investigators
2. Current, dated Institutional Review Board (IRB) membership list

3. Written documentation of IRB protocol approval (protocol number/title and approval date) and Informed Consent Form (protocol number/title and approval date)
4. A copy of the IRB-approved Informed Consent Form (The Informed Consent Form must be reviewed by the study Principal Investigator prior to IRB submission.)

## Study Completion

The following data and materials must be on file at the study site before the study can be considered complete or terminated:

1. Completed electronic case report forms (eCRFs) for all study subjects.
2. All regulatory documents including:
  - a. *Curriculum vitae* for each investigator and study staff member.
  - b. Signed confidentiality agreement
  - c. Study protocol and protocol amendments
  - d. Institutional Review Board approval letter (s) for initial protocol and any protocol amendments; as well as continuing review approval letters.
  - e. All Institutional Review Board correspondence
  - f. Study termination letter
  - g. Institutional Review Board membership list
  - h. Site personnel signature list
  - i. Financial Disclosure and Conflict of Interest forms for all site investigators
  - j. Patient screening and enrollment logs
  - k. Signed study Informed Consent Forms for each subject
  - l. Supporting source documentation for values and responses in case report forms
  - m. Supporting source documentation for adverse events

## Informed Consent

A template for the Informed Consent Form will be provided to the study site by the Study Coordinating Center. The Informed Consent Form must be signed by the subject or his or her legally authorized representative before enrollment into the study. A hardcopy of the Informed Consent Form must be provided to the subject or his or her legally authorized representative. If applicable, informed consent should be obtained using Interpreter Services. If an interpreter is required to explain the study, the informed consent presented to the patient for signature must be in the language in which the patient is literate.

Signed Informed Consent Forms must remain in each subject's study file and be available for verification by the Study Sponsor at all times. Documentation of the date informed consent was obtained and a notation that a signed copy of the

Informed Consent Form was provided to the study subject should be recorded. The informed consent process must always be conducted in a non-coercive manner.

### **Disclosure of Data**

Subject data obtained for this study will be maintained as confidential, and disclosure to parties other than study personnel will be prohibited. Upon the study subject's permission, medical information may be given to his or her physician or other medical personnel for his or her welfare.

### **Retention of Records**

Records and documents pertaining to the conduct of this study including case report forms, signed informed consent forms, protocol and amendments, supporting source documentation for values and responses in the case report forms, and supporting documentation for adverse events must be retained by the investigators for at least two years after conclusion of the study.

### **Feasibility**

#### **Brigham and Women's Hospital**

Brigham and Women's Hospital (BWH) is a 777-bed acute tertiary care facility providing medical and surgical care for patients with general medical, cardiothoracic, orthopedic, oncologic, neurologic, obstetric, gynecologic, and gastrointestinal conditions. BWH's affiliation with the Dana Farber Cancer Institute (DFCI) has resulted in a large population of oncology patients receiving care in the inpatient wards and in the Cardiovascular Medicine clinics. DFCI provides care to a large population of MM patients who travel from around the world. With the opening of the Heart and Vascular Center in 2014, BWH has solidified its position as a world leader in cardiovascular care and research, supporting an integrated care model in a single location. BWH is one of the world-leaders in the rapidly growing field of cardio-oncology. [name] cardiovascular medicine outpatient practice, which is based in the Heart and Vascular Center, includes a large number of referrals for thrombosis in the setting of malignancy.

#### **The BWH Thrombosis Research Group**

The Thrombosis Research Group, directed by [name], Professor of Medicine, Harvard Medical School and Section Head of Vascular Medicine at Brigham and Women's Hospital, is based at BWH and Harvard Medical School. The Thrombosis Research Group has a decades-long

commitment to improving the care for patients with cancer and increased thrombosis risk.

The Thrombosis Research Group has an infrastructure of experienced leadership, with trained personnel in a multidisciplinary academic team (pharmacists, fellows, research nurses, research coordinators, biostatisticians, administrators, and medical informatics specialists). Data storage and computing resources, as well as a network of regional, national, and international collaborating investigators, facilitate our execution of ongoing research projects and our planning of future research projects. The Thrombosis Research Group has studied all aspects of thrombosis in malignancy, including epidemiology, diagnosis, and VTE prevention. According to [www.pubmed.gov](http://www.pubmed.gov), the Group has authored more than 90 Original Reports since 2010. [name] appreciates the burden of thrombosis on the cancer population through registries that he has led (14) and high-impact reviews that he has published on the subject (7,15). Drs. [name] and [name] have extensive experience leading large randomized controlled trials focused on prevention of thromboembolic disease. Examples of major Thrombosis Research Group-led trials in thrombosis prevention include the 2500-patient multicenter Electronic Alert Trial (16), the 2500-patient multicenter Physician Alert Trial (17), and the 2500-patient Discharge Alert Trial (18).

For this trial, the Clinical Coordinating Center of the Thrombosis Research Group will draft and finalize the study protocol, informed consent, and case report form, obtain Institutional Review Board approval, create an electronic data repository, assist the clinical centers with local IRB approval, file the IND, ensure scientific and financial integrity, approve site payments, plan and host an Investigators Meeting, perform the data analysis, and draft and submit for publication the study manuscript.

### **Vanderbilt Cardio-Oncology Program**

Vanderbilt University Medical Center will be the Study Enrollment Center. The proposed study will be feasible because Vanderbilt is a large Center of Excellence for MM care with active clinical research programs. Specifically, the Vanderbilt Cardio-Oncology program, directed by [name], brings together physicians and scientists with a focus on cardiac, vascular and thrombotic complications that occur as a result of cancer and cancer therapies. The integrative and collaborate nature of the Vanderbilt Cardio-Oncology program is illustrated by the care of MM patients. The laboratory of [name] is investigating the mechanisms of vascular and thrombotic toxicity associated with IMiDs and PIs. At the same time, the group is already embarking on several clinical and translation studies focused on cardiovascular effects of MM treatments. [name], Director of Cardio-Oncology at Vanderbilt University Medical Center will work closely with colleagues in oncology, including [name]. [name] in spearheading the recruitment effort.

## **Potential Risks and Benefits**

### **Potential benefits to the subject**

The potential benefit of prophylaxis with apixaban in patients with MM receiving IMiDs is prevention of VTE, including fatal PE.

### **Potential Benefits to Society**

The major potential benefit to society of the proposed trial of apixaban for primary prevention of VTE in patients with MM receiving IMiDs is that if successful, the study will provide the foundation for a novel regimen that avoids the discomfort of the currently used injectable anticoagulant strategies. The data acquired from the current study will inform the design of a larger randomized controlled trial focused on clinical outcomes.

### **Potential Risks to the Subject**

The foreseeable risk of apixaban for primary prevention of VTE in patients with MM receiving IMiDs is major or clinically relevant non-major bleeding.

